3.1.2.2 Phase 1 Dose Escalation Extended Treatment Period

Patients from the Phase 1 dose escalation combination cohorts are allowed to continue to receive APX005M in combination with nivolumab and/or cabirizumab at the same dose levels until disease progression, unacceptable toxicity, or other reason for treatment discontinuation.

If a complete response (CR) is achieved, patients will be allowed to continue on therapy until disease progression, unacceptable toxicity, or other reason for treatment discontinuation.

3.1.2.3 Phase 1b Expansion Cohorts

To further characterize safety and efficacy of APX005M in combination with nivolumab and cabirizumab, Phase 1b will enroll patients of 3 advanced cancer types: melanoma, NSCLC, and RCC. Enrollment in Phase 1b will begin when an RP2D for APX005M has been identified based on overall safety, tolerability, PK, and PD (if available) data.

During enrollment of any expansion cohort, if the observed number of responses makes it unlikely to achieve a target response rate for that indication, then further recruitment to that cohort may be suspended or terminated.

3.1.3 End-of-Treatment Follow-up Period

All patients should return to the clinic 28 (± 7) days and 100 (± 7) days from their last dose of study drug to complete the End-of-Treatment Follow-up Period, irrespective of whether a patient is discontinued from the study drug at a planned visit or mid-cycle. AEs will be assessed until resolution, return to baseline, or are stabilized per treating Investigator's assessment. Adverse event reporting will continue until 100 (± 7) days after the last dose of study drug or until initiation of subsequent anti-cancer therapy.

3.1.4 Long-Term Follow-up

Patients should continue onto Long-Term Follow-up after completing the End-of-Treatment Follow-up Period.

Patients will be followed every 12 weeks for survival, or more frequently as needed. Patients who discontinue treatment while showing clinical benefit (CR, partial response [PR], or stable disease [SD]) should have tumor assessments during these visits for duration of response.

Long-term Follow-up for survival may be conducted by telephone, rather than by an in-person visit, once tumor progression is determined or use of subsequent anti-cancer therapy has been initiated. During the Long-Term Follow-up Period, if the patient undergoes local therapy (e.g., resection, radiation) or new systemic therapy is initiated, this should be documented.

3.1.5 Study Duration

Patients who receive study drug(s) may continue as long as they experience clinical benefit in the opinion of the Investigator or until unacceptable toxicity or symptomatic deterioration attributed to disease progression as determined by the Investigator after an integrated assessment of radiographic data, biopsy results (if available), and clinical status, or withdrawal of consent. The maximum time allowed time on study treatment will be up to 2 years unless the study is terminated sooner by the Sponsor.

3.1.6 Stopping Rules

3.1.6.1 Stopping Rules for All Cohorts

Management of drug-related toxicities and laboratory abnormalities will follow the guidelines outlined in Section 4.8 and Section 4.9.

The Sponsor will discuss such cases with the Industry Collaborators as appropriate to determine further enrollment. IRBs may be notified by the Sponsor of all cases and decisions regarding continued enrollment, according to applicable regulatory requirements or institution procedures.

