2.2 Phase 1b Objectives

2.2.1 Primary

- To determine the objective response rate (ORR) using RECIST v1.1 to APX005M in combination with cabiralizumab and nivolumab in 3 separate patient cohorts: advanced melanoma, NSCLC, and RCC whose tumors are resistant to anti-PD-1/PD-L1 therapy
- To evaluate the safety and tolerability of the RP2D of APX005M in combination with cabiralizumab and nivolumab

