For the purpose of dose escalation, we will require a 28 day observation period from the time the last patient in a given cohort was treated. For the purpose of calculating the MTD, we will require a minimum of 28 days of observation for each patient.

Dose escalation in Phase 1 will proceed as follows:

If none of the first 3 evaluable patients in a dose cohort experience a DLT in the first two cycles, then the next 3 patients will be treated at the next higher dose cohort. If 1 of 3 patients within a cohort experiences a DLT in the first two cycles, then 3 additional patients will be added to that cohort. If a second patient experiences a DLT at that dose level in the first two cycles, the next cohort will not be initiated, and the dose of one or more drugs will be de-escalated. Patients at each dose level will be evaluated for at least 28 days from the start of treatment before additional patients can be treated at a higher dose level. If DLTs are observed in 2 or more patients within a cohort, the maximum tolerated dose (MTD) will have been exceeded and no further patients will be treated at that dose level.

DLT evaluation and enrollment decisions will follow the guidance in Table 3.

Table 3: Algorithm for Dose-Escalation Decisions

Number of Patients with DLT at a Given Dose Level	Dose Escalation Decision Rule
0/3	Escalation will occur into the next highest dose cohort
1/3	Enroll 3 additional patients at current dose level
$\geq 2/3$	Stop enrollment. Enroll 3 more patients at the lower dose level, if only 3 were previously entered, or at an intermediate dose level.
1/6	Open next cohort
$\geq 2/6$	Stop enrollment. Enter 3 more patients at the lower dose level at an intermediate dose level.

Dose escalation will continue until either the MTD or maximum planned dose of APX005M is reached, with a minimum of 3 patients enrolled in each cohort.

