3.2 Study Population

3.2.1 Planned Number of Patients

In the Phase 1 dose escalation portion of the trial, we will enroll at least 3 patients per cohort. There are a total of 6 cohorts. In the Phase 1b portion, a Simon two stage design will be used. At least 13 patients per each disease cohort (advanced melanoma, NSCLC, and RCC) will be enrolled in the first phase and in the second phase, an additional 21 patients per disease cohort, for a maximum of 34 patients per disease cohort, are expected to be enrolled, for a total of 102 subjects.

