4.3 Method of Assigning Patient Identification

Patients must be able to provide written informed consent and meet all eligibility criteria. No waivers of inclusion or exclusion criteria will be granted by Sponsor or its designee for any patient enrolled in the study. Before enrolling a patient, all eligibility criteria must be satisfied.

See Section 4.4.1 and Figure 6 for dosing schema. Patients who qualify for Phase 1 dose escalation of the study will be enrolled as follows:

- Cohort 1 will be enrolled first and these patients will be followed one 14-day cycle.
- Once the DLT follow-up period of 28 days is cleared for Cohort 1, simultaneous enrollment to Cohort 2 and Cohort 3 will occur. Patients in these cohorts will be treated for a total of one 14-day cycle.
- Simultaneous enrollment into Cohort 4 and Cohort 5 will proceed once the 14-day DLT

period for dose escalation is cleared in the preceeding Cohorts 2 and 3.

- Once the DLT period of 28 days for dose escalation is cleared Cohorts 4 and 5, enrollment to the final Cohort 6 will occur.
- The MTD will be calculated for patients who have received at least 2 cycles (at least 28 days) of study drug.
- Dose escalation into sequential dose levels of APX005M in combination with cabiralizumab and nivolumab may proceed until DLTs are observed either in the cabiralizumab/APX005M doublet therapy cohorts 1, 3, and 5 or in the nivolumab/cabiralizumab/APX005M triplet therapy cohorts after discussion and agreement between the PIs and Industry Collaborators.

In Phase 1b, a maximum of 34 patients will be enrolled per disease-specific cohort (advanced melanoma, NSCLC, or RCC). Enrollment will be open for all cohorts in parallel and will continue until the enrollment target is reached. Once a disease cohort is filled, further enrollment will be restricted to the cohort(s) that have not been filled. A total of approximately 102 patients will be enrolled in the Phase 1b arm of the study.

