9.1.2 Yale Safety Reporting and Monitoring (DSMP)

The PI and IND holders will monitor the clinical trial for safety. The PI will assess all expedited adverse events and will periodically review all adverse events observed on the trial. Yale Cancer Center standard operating procedures (SOPs) for assessment and reporting of adverse events are followed which are in compliance with 21 CFR 312.32 and 312.22.

The clinical trial data consisting of all required observations, AEs, and laboratory data are entered into a computerized database in a timely manner. The accuracy and completeness of the database, timely submission of SAEs and compliance with the protocol, is assured by periodic auditing conducted by the Yale Cancer Center Office of Protocol Review and Monitoring, which reports to the Yale Data Safety & Monitoring Committee (DSMC). Safety data will be submitted to the DSMC at least once yearly or more often as required by the DSMP. The DSMC will conduct an internal audit of the study every 6-12 months, per institutional requirements. On a regular interval basis, status reports of all laboratory parameters, AEs and SAEs are reviewed by the PI to view composite data across subjects. Regular meetings are held to discuss ongoing patient treatment and adverse events.

Expedited SAE reports submitted by the Investigator to FDA are also copied to the HIC and other relevant institutional safety committees within the timeframes required by Yale. These will also be copied to BMS and Apexigen. The Principal Investigator will distribute manufacturer-provided safety reports and updated Toxicity Lists to the institution's HIC and all relevant

personnel involved in the conduct of the study. The Toxicity List, in addition to the Investigator's Brochure, will be used as a reference for reporting any new SAE.

Possible actions taken by the PI or the Yale DSMC if a new unexpected toxicity is identified from the above safety review, or if the periodic review of all adverse events and laboratory data indicates a pattern of incidence or severity of toxicity that raises a safety concern, can be to:

1. Revise consent form
2. Amend the protocol
3. Suspend the protocol

All AEs found to be expected or non-serious, will be included in the Annual Report. AEs considered to be serious will be communicated to the industry collaborators Bristol-Myers Squibb and Apexigen within 24 hours.

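### Section 3.1.6.1 defines no stopping rule, and phase 1b has no pre-specified toxicity boundary although RP2D safety is a primary objective

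*Combined protocol and SAP*

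**What the plan says.** Section 3.1.6.1 makes two substantive statements. The first concerns individual patients: "Management of drug-related toxicities and laboratory abnormalities will follow the guidelines outlined in Section 4.8 and Section 4.9". The second concerns accrual: "The Sponsor will discuss such cases with the Industry Collaborators as appropriate to determine further enrollment". It adds that IRBs may be told of cases and decisions. Nothing in the section says what a case is.

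Section 2.2.1 lists two primary objectives for phase 1b. One is ORR. The other is "To evaluate the safety and tolerability of the RP2D of APX005M in combination with cabiralizumab and nivolumab".

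Phase 1b is much larger than any escalation cohort. Section 3.2.1 plans "for a maximum of 34 patients per disease cohort, are expected to be enrolled, for a total of 102 subjects", and under Section 4.3 "Enrollment will be open for all cohorts in parallel and will continue until the enrollment target is reached". Escalation runs "with a minimum of 3 patients enrolled in each cohort" (Section 3.1.2.1). After one DLT in three patients, "then 3 additional patients will be added to that cohort".

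Oversight is described in Sections 6.2.1 and 9.1.2. The PI reviews laboratory data, AEs and SAEs across subjects at regular intervals, and regular meetings discuss adverse events. For the DSMC, "Safety data will be submitted to the DSMC at least once yearly or more often as required by the DSMP", and it audits the study every 6 to 12 months. The PI or DSMC can revise the consent form, amend the protocol or suspend it if a new unexpected toxicity, or the pattern of toxicity, gives cause for concern.

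**The concern.** ORR has an exact rule in each disease cohort. Safety, listed beside it as primary, has none. A 3+3 cohort carries little information on the DLT rate, so expansion is where a rate above the protocol's own 33% ceiling would most probably show itself. The accrual stops in expansion react only to too few responses. A regimen that is active but too toxic would pass all of them, and whether accrual paused would rest on judgement made as the data came in, with nothing fixed beforehand. At stake is the exposure of most of the trial's patients.

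**Working it through.** **Where toxicity rules apply.**

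- Section 3.1.2.1, Table 3 and the MTD definition (DLTs in at most 33% of patients): phase 1 escalation.
- Section 3.1.2.1.1, DLT definition and the list of toxicities that bar progress: advancing to later escalation cohorts.
- Section 3.1.2.3: a phase 1b cohort may be suspended or terminated on the observed number of responses.
- Section 7.1: a cohort stops at 1 or fewer responses in 13.
- Section 4.9, Table 5: hold or discontinue drug in the individual patient.
- Section 7.4: safety is tabulated, with no threshold or interim look.

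None of these is a toxicity boundary on phase 1b accrual.

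**The plan's own figures.** Inputs from Section 7.1: 13 then 34 patients, stop at ≤1/13, reject at ≥6/34, response rates 10% and 25%. Exact enumeration gives type I error 0.0957 and power 0.811, in line with the stated 0.1 and 80%. The maximum is 3 × 34 = 102. The probability of stopping at stage 1 is 0.621 at 10% and 0.127 at 25%, so expected enrolment over three cohorts is 63 and 94. These stops do not depend on toxicity.

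**What one escalation cohort shows.** With true DLT rate q, a cohort clears on 0/3, or on 1/3 followed by 0/3:

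P(clear) = (1−q)³ + 3q(1−q)² × (1−q)³ = (1−q)³ + 3q(1−q)⁵

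- q = 0.33: 0.43
- q = 0.40: 0.216 + 1.2 × 0.07776 = 0.31
- q = 0.50: 0.125 + 1.5 × 0.03125 = 0.17

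Exact one-sided 95% upper bounds on the DLT rate are 63% after 0/3 and 58% after 1/6. Both lie well above 33%.

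**Illustrative boundary.** The prior, cutoff, pooling and look schedule are assumptions made here; the plan gives none. With prior Beta(0.33, 0.67) and x DLTs in n pooled patients, the posterior is Beta(0.33 + x, 0.67 + n − x). Pause when Pr(rate > 0.33) > 0.95, checked after every patient from the sixth. Example limits are 6/10, 11/20 and 15/30. An exact recursion, counting a pause as the end of accrual, gives:

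| True DLT rate | P(pause), up to 102 patients | Expected patients |
|---|---|---|
| 15% | 0.002 | 102 |
| 20% | 0.01 | 101 |
| 25% | 0.04 | 98 |
| 30% | 0.13 | 92 |
| 33% | 0.24 | 85 |
| 40% | 0.67 | 57 |
| 50% | 0.99 | 23 |

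If all three cohorts stop at stage 1 (3 × 13 = 39 patients), the pause probability is 0.43 at 40% and 0.83 at 50%.

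**Sensitivity.** Looks every 6 patients, other settings unchanged, give 0.61 at 40% and 0.98 at 50%. The recursion assumes that each outcome is known before the next enrolment. If 10 more patients enrol before a crossing is recognised (an assumption), expected numbers rise from 57 to 64 at 40% and from 23 to 33 at 50%.

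**The case against.** The strongest reply is that the trial is not unsupervised. The PI sees cross-subject safety data regularly, SAEs reach the PI within 24 hours, the DSMC audits every 6 to 12 months, and the protocol can be suspended. This stands. A reader of 3.1.6.1 alone might infer that nothing could stop the expansion; Sections 6.2.1 and 9.1.2 do not support that. What is missing is a criterion fixed in advance.

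A reader might also infer from the yearly DSMC minimum that its review would come after most accrual. The documents give no accrual rate, so this cannot be concluded.

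The 3+3 figures describe one cohort in isolation. Cohort 6 opens only after Cohorts 4 and 5 have been observed, certain toxicities bar advancement, and the RP2D may be set below the MTD. So 0.31 is not the probability that a dose with a 40% DLT rate becomes the RP2D.

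The figure of 102 is a ceiling. Patients treated at the MTD in escalation are carried over (Section 7.1), so if 3 to 6 are carried over, 96 to 99 would be new. Futility stops can lower the total further.

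Finally, Section 2.2.1 makes safety a primary objective but no formal co-primary test exists, and applying the 33% limit to expansion is a proposal of this review. Both remarks are fair. Neither supplies the missing boundary.

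**Conclusion.** The point holds as a gap in pre-specification. Section 3.1.6.1 promises stopping rules and defines none, and no numerical toxicity boundary applies to phase 1b anywhere in the document. Oversight is real but discretionary. The triplet dose may be cleared on 3 to 6 patients in its own cohort, which cannot exclude DLT rates near 60%.

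The benefit of a boundary depends on the true rate and on how far accrual runs: a pause probability of 0.67 to 0.99 at true rates of 40% to 50% with 102 patients, and 0.43 to 0.83 with 39. These figures rest on the illustrative prior and cutoff, pooling of the three diseases, and immediate knowledge of DLT status. The 28-day DLT window and parallel accrual would delay a pause and raise the expected numbers. The change is worth making because it is cheap and protects most of the trial's patients; the trial's efficacy design is unaffected.

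**What to change.** In Section 3.1.6.1, state that DLTs as already defined in Section 3.1.2.1.1 are tallied for all patients treated at the RP2D, including those carried over from escalation. State that accrual pauses for DSMC review when the count crosses a pre-computed boundary against the existing 33% limit. Print the boundary table and its operating characteristics. The sponsor should set the prior, cutoff, pooling across diseases and look schedule, and say how patients still inside the 28-day window are counted. Refer to the same rule in Sections 7.4 and 9.1.2. No dose or patient-level management rule changes.

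The cost is a table, a running tally and some pauses at rates within the limit. For the illustration these have probability 0.01 at 20%, 0.04 at 25%, 0.13 at 30% and 0.24 at 33%. A sponsor who finds the last two too high can raise the cutoff, at the price of slower detection at 40%.

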3.1.6.2 Treatment Beyond Progression

Accumulating clinical evidence indicates that the emergence of objective responses to agents that activate anti-tumor immune responses may follow delayed kinetics of weeks or months, and can be preceded by initial apparent progression of disease with the appearance of new lesions or some enlarging of lesions while certain index lesions are regressing (“mixed response”). Therefore, it is reasonable to allow patients who experience apparent progression to continue to receive treatment until progression is confirmed at the next imaging assessment. These considerations should be balanced by clinical judgment as to whether the patient is clinically deteriorating and unlikely to receive any benefit from continued treatment.

Such deterioration will be assessed to have occurred after a clinical event that, in the Investigator’s opinion, is attributable to disease progression and is unlikely to reverse with continued study treatment and therefore indicates that the patient is not benefiting from study treatment and cannot be managed by the addition of supportive care. The decision to continue treatment should be discussed with the PI.

3.2 Study Population

3.2.1 Planned Number of Patients

In the Phase 1 dose escalation portion of the trial, we will enroll at least 3 patients per cohort. There are a total of 6 cohorts. In the Phase 1b portion, a Simon two stage design will be used. At least 13 patients per each disease cohort (advanced melanoma, NSCLC, and RCC) will be enrolled in the first phase and in the second phase, an additional 21 patients per disease cohort, for a maximum of 34 patients per disease cohort, are expected to be enrolled, for a total of 102 subjects.

3.2.2 Inclusion Criteria for All Cohorts

1. Biopsy proven metastatic melanoma, NSCLC or RCC whose disease has progressed on anti-PD(L)-1 therapy without any intervening therapy. Progression will be determined by the investigator based on clinical and/or radiographic features. Additional requirements as below:

Melanoma:

- Unresectable stage III or stage IV melanoma, irrespective of *BRAF* status, with histologic or cytologic confirmation

RCC:

- Histologic or cytologically documented, locally advanced unresectable or metastatic RCC irrespective of histologic subtype

NSCLC:

- Histologic or cytologically documented, locally advanced or metastatic (i.e. Stage IIIB not eligible for definitive chemoradiotherapy, stage IV, or recurrent) NSCLC.

- Patients known to harbor an ALK rearrangement or EGFR mutation known to be sensitive to FDA-approved tyrosine kinase inhibitors (TKI), are only eligible after experiencing disease progression (during or after treatment) or intolerance to an FDA approved ALK TKI or EGFR TKI, respectively.
- Patients with TKI-treated EGFR mutant NSCLC harboring the secondary EGFR T790M tumor must have received prior osimertinib.
- Patients with crizotinib-treated ALK rearranged NSCLC must have received a next generation ALK inhibitor.

2. At least 1 site of disease must be accessible to provide repeat biopsies for tumor tissue. This site may be a target lesion as long as it will not be made unmeasurable by the biopsy procedure. Subjects may forgo the pretreatment biopsy if 1) an entire archival FFPE tumor block is available that was taken after the last systemic therapy was administered or 2) if the Investigator deems that the subject does not have tumor in a site that is amenable to biopsy.

3. Age ≥ 18 , able to understand and sign the informed consent form

4. ECOG performance status < 2

5. Any number of previous treatments. Other prior systemic therapies must have been administered at least 4 weeks before administration of the study drugs; the exception to this is molecular targeted therapies which must have been administered at least 2 weeks prior to the start of the study drugs or after 5 half-lives have occurred, whichever is shorter.

6. Life expectancy of at least 6 months

7. A history of previously treated brain metastases is allowed, provided that they are stable for at least 4 weeks.

8. Willingness to undergo mandatory tumor biopsy prior to initiation of therapy and before the fifth cycle.

9. Willingness to provide an archival specimen block, if available, for research.

10. Patients must have normal organ and marrow function as defined below:

System	Laboratory Value
Hematological	
Absolute neutrophil count (ANC)	$\geq 1,500 / \mu\text{L}$
Platelets	$\geq 100,000 / \mu\text{L}$
Hemoglobin	$\geq 9 \text{ g/dL}$ or $\geq 5.6 \text{ mmol/L}$ without transfusion or EPO dependency (within 7 days of assessment)
Renal	
Serum creatinine OR Measured or calculated ^a creatinine clearance (GFR can also be used in place of	$\leq 1.5 \times$ upper limit of normal (ULN) OR $\geq 50 \text{ mL/min}$ for subject with creatinine levels $> 1.5 \times$ institutional ULN

creatinine or CrCl)	
Hepatic	
Serum total bilirubin	$\leq 1.5 \times \text{ULN}$ OR Direct bilirubin $\leq \text{ULN}$ for subjects with total bilirubin levels $> 1.5 \text{ ULN}$
AST (SGOT) and ALT (SGPT)	$\leq 2.5 \times \text{ULN}$
Albumin	$\geq 2.5 \text{ mg/dL}$
Coagulation	
International Normalized Ratio (INR) or Prothrombin Time (PT)	$\leq 1.5 \times \text{ULN}$ unless subject is receiving anticoagulant therapy as long as PT or PTT is within therapeutic range of intended use of anticoagulants
Activated Partial Thromboplastin Time (aPTT)	$\leq 1.5 \times \text{ULN}$ unless subject is receiving anticoagulant therapy as long as PT or PTT is within therapeutic range of intended use of anticoagulants

^aCreatinine clearance should be calculated per institutional standard.

11. Female subject of childbearing potential should have a negative urine or serum pregnancy within 24 hours prior to receiving the first dose of study medication. If the urine test is positive or cannot be confirmed as negative, a serum pregnancy test will be required.
12. Female subjects of childbearing potential should be willing to use a highly effective contraception (hormonal or IUD) or be surgically sterile, or abstain from heterosexual activity for a period of at least 5 months after the last dose of study drug. Subjects of childbearing potential are those who have not been surgically sterilized or have not been free from menses for > 1 year.
13. Male subjects should agree to use an adequate method of contraception starting with the first dose of study therapy through at least 7 months after the last dose of study drug.
14. Patients must have at least one measurable lesion at baseline by computed tomography (CT) or magnetic resonance imaging (MRI) as per RECIST v1.1 criteria.
 - a. Tumor sites situated in a previously irradiated area, or in an area subjected to other loco-regional therapy, are not considered measurable unless there has been demonstrated progression in the lesion.
15. Prior focal radiotherapy must be completed before first dose of study drug administration, although palliative radiation may be allowed on treatment (see permitted concomitant therapies below). Radiation to pulmonary or intestinal sites must be completed at least 4 weeks prior to study Day 1. There is no time restriction prior to study Day 1 for patients who have received radiation to bone, soft tissue sites or other sites. No radiopharmaceuticals (strontium, samarium) within 8 weeks before first dose of study drug administration.
16. Major surgery must be completed at least 4 weeks before first dose of study drug administration. Surgery requiring local/epidural anesthesia must be completed at least 72 hours before first dose of study drug administration and patients should have recovered. Surgical wounds must be healed.

